6.4 Treatment compliance

During the Initial Treatment Period, IMP will be administered by a health care professional and compliance will be determined at the visit by the health care professional. Drug accountability must be recorded on the Drug Accountability Form.

During the OLE Period, Dose A of the IMP may be administered by a health care professional, caregiver, or study participant as detailed in Section 6.2. Dose B will be administered by a health care professional, to ensure accurate dosing of the lower volume of IMP. All used syringes (Dose A and Dose B) and vials (Dose B only) will be disposed of as detailed in Section 6.2.1. Dates, body locations, kit numbers, and time of administration will be documented either by caregiver, participant (once he/she becomes 18 years of age) or health care professional where applicable. Home administration documentation should be reviewed by the Investigator.

If a participant is noncompliant with the study procedures or medications that may present a risk to the safety of the participant in the opinion of the Investigator, then the participant should be withdrawn as described in Section 7.2.

6.5 Concomitant medications/treatments

All concomitant medications and interventions administered during the study will be recorded on the appropriate eCRF pages.

6.5.1 Permitted concomitant treatments (medications and therapies)

The use of concomitant medications for medical conditions (eg, diabetes, acute infections) or treatment of an AE is permitted during this study as long as medications are not explicitly prohibited by the protocol.

The following concomitant medications are permitted during the study:

- Nonsteroidal anti-inflammatory drugs, acetaminophen, paracetamol, and opioids, as appropriate for the study participant.
- Keratolytics and coal tar for PSO in the OLE Period (ie, from Week 20 onwards).
- Study participants may continue to use topical moisturizers or emollients, bath oils, or oatmeal bath preparations for skin conditions during the study, as needed.
- As needed (PRN) use of mild (Class VII) to moderate (Class IV) potency topical corticosteroids for PSO is permitted in the OLE Period (ie, from Week 20 onwards) at the Investigator's discretion.
- As needed (PRN) use of treatment for scalp PSO, such as shampoo. If this treatment contains a corticosteroid, it must adhere to the guidance for topical corticosteroids outlined in the above bullet.
- Vitamin D analogs, topical retinoids, and topical calcineurin inhibitors (if appropriate for the participant) for PSO during the OLE Period (ie, from Week 20 onwards).

6.5.2 Prohibited concomitant treatments (medications and therapies)

For prohibited prior medications, refer to the exclusion criteria (Section 5.2).

The following concomitant medications and therapies are prohibited during the study:

- Systemic agents:
 - Systemic retinoids
 - Systemic immunosuppressant agents (eg, methotrexate, cyclosporine, azathioprine, thioguanine)
 - Systemic fumarate
 - Systemic corticosteroids
 - Any other antipsoriatic agent (systemic) under investigation (or approved after the protocol is approved)
- Photo/chemotherapy
- Biologic therapies (other than bimekizumab)
- Topical agents for dermatologic use:

- High potency topical corticosteroids (Class I, II, and III)
- Any other antipsoriatic agent (topical) under investigation
- Mild (Class VII) to moderate (Class IV) potency topical corticosteroids before Week 20
- Keratolytics and coal tar for PSO before Week 20
- Vitamin D analogs, topical calcineurin inhibitors, and topical retinoids for PSO before Week 20

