The potential risks to adolescent participants in this study include exposure to bimekizumab, with the potential for AEs. The 2 selected dosing regimens have been well-tolerated by adult study participants with PSO, and permit quantification of plasma concentrations. Additional design measures to minimize the burden of participating in this clinical study include: no exposure to placebo, both dose regimens anticipated to provide efficacy that is equivalent to or better than standard of care, and the allowance of permitted concomitant treatment options. The PS0020 study design further ensures that adolescents not benefitting from study participation are withdrawn quickly (ie, if IGA is ≥ 3 at Week 20) so that they can receive the appropriate alternate therapy outside of the study. A DMC will monitor safety and assess the benefit-risk balance throughout the conduct of the study.

Subcutaneous injection and blood collection may cause distress, pose risks, and are a potential burden to participants. The collection of blood samples and volumes has been minimized to alleviate distress, burden, and risks to participants as much as possible (eg, butterfly needles), and by allowing Screening safety laboratory assessments to be used as Baseline assessments. The blood sampling scheme was designed to collect the minimum number of blood samples needed to accurately and completely describe the PK of bimekizumab. This minimizes the number of venipunctures and the total volume of blood collected from each participant during the study. The planned total blood volumes collected for this study will not exceed the limits recommended in the Ethical Considerations for Clinical Trials on Medicinal Products conducted with the Paediatric Population (European Union, 2008).

Investigational sites selected for participation in PS0020 will employ Investigators and personnel who are experienced and well-trained to conduct research studies. Furthermore, they will be experienced in dermatology and in International Council for Harmonisation (ICH) Good Clinical Practice (GCP) regulated clinical research.

Investigators are expected to continually assess the balance of burden to each participant against the observed and anticipated clinical benefit, and to recommend study withdrawal if the benefit-risk balance is not favorable.

More detailed information about the known and expected benefits and risks and reasonably expected AEs of bimekizumab may be found in the IB.

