- Any other laboratory abnormality, which, in the opinion of the Investigator, will prevent the participant from completing the study or will interfere with the interpretation of the study results. Individual screening tests for which the results are in error, borderline, or indeterminate for inclusion in the study can be repeated once for confirmation during the Screening Period. Upon retesting, participants whose results remain outside this threshold should not be randomized.

Prior/Concomitant therapy

17. Participant has previously participated in this study or has received bimekizumab in another study.
18. Participant has received drugs listed in [Table 5-1](#) outside the specified timeframes relative to the Baseline Visit or receives prohibited concomitant treatments (see Section 6.5.2).

Table 5-1: Exclusions for prior treatments

Drug class	Dose	Washout period relative to Baseline Visit
Systemic retinoids	Any dose	4 weeks
Systemic treatment (non-biological) Systemic immunosuppressant agents (eg, methotrexate, cyclosporine, azathioprine, thioguanine) Systemic fumarate/fumaric esters specifically used for treatment of PSO Systemic corticosteroids Photo/chemotherapy	Any dose	4 weeks
Anti-TNFs Adalimumab Infliximab, golimumab, certolizumab pegol (including biosimilars for any of these anti-TNFs) Etanercept (including biosimilar)	Any dose	12 weeks for infliximab, golimumab, adalimumab, certolizumab pegol 4 weeks for etanercept

Table 5-1: Exclusions for prior treatments

Drug class	Dose	Washout period relative to Baseline Visit
Other biologics and other systemic therapies: Ustekinumab Briakinumab Apremilast, tofacitinib Alefacept, efalizumab, guselkumab Rituximab	Any dose	24 weeks for ustekinumab and briakinumab 2 weeks for apremilast/tofacitinib 12 weeks for alefacept, efalizumab, and guselkumab 52 weeks for rituximab
Anti-IL-17 therapy (including ixekizumab and secukinumab)	Any dose	12 weeks (any prior use of bimekizumab is excluded)
Any other antipsoriatic agent (systemic) under investigation (or approved after the protocol is approved)	Any dose	12 weeks (or 5 half-lives, whichever is longer)
Topical agents (except as outlined in Section 6.5.1) Topical corticosteroids for dermatological use Vitamin D analogs, topical retinoids, and topical calcineurin inhibitors Keratolytics and coal tar	Any dose	2 weeks
Any other topical antipsoriatic agent under investigation	Any dose	4 weeks

IL=interleukin; PSO=psoriasis; TNF=tumor necrosis factor

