6.8 Treatment after the end of the study

Study participants will be scheduled to have the SFU Visit 20 weeks after the final injection of IMP (the final dose of IMP may be administered in the Initial Treatment Period or in the OLE Period). During the SFU, if study participants' PSO deteriorates, the Investigator may consider standard of care for PSO treatment after discussion with the Medical Monitor or UCB Study Physician. Note that the half-life of bimekizumab must be considered in selection of appropriate PSO treatments during the SFU Period. All concomitant medications and PSO interventions administered during the SFU will be recorded on the appropriate eCRF pages.

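### A response reached on IMP plus another psoriasis treatment that should not have been started counts as a bimekizumab response, and no planned sensitivity analysis is aimed at this

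*Protocol*

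**What the plan says.** **Prohibited treatment.** Protocol 6.5.2 bars systemic retinoids, immunosuppressants, fumarate and corticosteroids, photo/chemotherapy, biologics other than bimekizumab, and, as a residual line, "Any other antipsoriatic agent (systemic) under investigation (or approved after the protocol is approved". It also bars topicals for a limited time, for example "Mild (Class VII) to moderate (Class IV) potency topical corticosteroids before Week 20".

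**Consequence of use.** Protocol 7.2 item 9 asks the Investigator to discuss possible withdrawal with the Medical Monitor when a participant takes something on the 6.5.2 list. Item 8, on noncompliance, leads to the same discussion. Neither makes stopping IMP mandatory.

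**Estimands.** Protocol 9.3.2.1 and SAP 5.4.1.2 define one intercurrent event for each secondary efficacy endpoint: discontinuation of IMP before the time point. For the binary endpoints a composite strategy applies. SAP 5.1.1.7.3 sets the response to nonresponse from the intercurrent event onward, even where data were observed.

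**Sensitivity analyses.** SAP 5.4.1.3 plans an observed-case (OC) analysis and a repeat in the PK-PPS. SAP 4.1.4 removes a participant from the PK-PPS for important deviations only if they would affect the drug concentration. SAP 5.1.1.10 nevertheless presents that set as the reasonably compliant one for efficacy. SAP 6.1.2 leaves the removal criteria to a separate Protocol Deviation Assessment Plan.

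**Data on use.** All concomitant medication goes into the eCRF (Protocol 6.5). SAP 6.1.4 plans summaries by ATC class, dose group and study period, plus a by-participant listing.

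**The concern.** The binary endpoints are meant to describe response to each bimekizumab dose. The protocol judges certain other psoriasis treatments serious enough to prohibit, but the analysis has no rule for a participant who takes one and stays on IMP. Any response then observed goes into the numerator for that dose.

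The main, OC and PK-PPS results could then agree without any of them testing this. Because SAP 5.1.1.10 describes the PK-PPS as reasonably compliant, a reader could take that agreement as robustness to noncompliance. Selected efficacy data are also among the inputs to the PS0021 dose decision (Protocol 9.7.1, SAP 5.9).

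**Working it through.** **Step 1. Apply the stated rules to a participant who starts another systemic antipsoriatic, or another psoriasis treatment prohibited by 6.5.2, before the time point.**

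| Situation | Main analysis | OC | PK-PPS by SAP definition |
|---|---|---|---|
| Stops IMP before the time point | Nonresponse (composite rule) | Not the gap at issue | Not the gap at issue |
| Stays on IMP, response observed | Responder | Responder | Responder, unless the deviation is held to affect concentration |
| Stays on IMP, no response observed | Nonresponder | Nonresponder | Nonresponder, or removed |

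Only the second row is a gap. OC addresses missing values, and here nothing is missing. The PK-PPS turns on bimekizumab concentration, and its definition does not mention a second drug acting on the skin.

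**Step 2. What if the unseen deviation plan did remove the user?** Removal takes the participant out of numerator and denominator. It does not recode the response. With 18 responders of 20 and one of them a user:

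- removed: 17/19 = 89.5%
- counted as nonresponder: 17/20 = 85%

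With 10 of 20, the figures are 9/19 = 47.4% and 9/20 = 45%.

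**Step 3. Size per participant.** Inputs: 20 per dose arm (Protocol 9.8, SAP 3) and the Clopper-Pearson 95% interval (SAP 5.1). The response rates are assumed for illustration. One flipped participant is worth 1/20 = 5 points at any rate.

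| Counted as planned | One user recoded |
|---|---|
| 18/20 = 90% (68.3 to 98.8) | 17/20 = 85% (62.1 to 96.8) |
| 15/20 = 75% (50.9 to 91.3) | 14/20 = 70% (45.7 to 88.1) |
| 10/20 = 50% (27.2 to 72.8) | 9/20 = 45% (23.1 to 68.5) |

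A user whose status would be the same either way moves the rate by 0.

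**Step 4. How often?** The documents give no frequency of use, so f below is an assumption. The chance of at least one user in an arm is 1 − (1 − f)^20. The largest expected shift is 20f users × 5 points, reached only if every user stays on IMP and flips.

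| f | Expected users per arm | Chance of at least one | Largest expected shift |
|---|---|---|---|
| 1% | 0.2 | 18.2% | 1 point |
| 2% | 0.4 | 33.2% | 2 points |
| 5% | 1.0 | 64.2% | 5 points |

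**Step 5. A side check of the drug lists.** Table 5-1 of Protocol 5.2 requires a washout of "2 weeks for apremilast/tofacitinib". Of the Table 5-1 entries, only these two drugs have no named or clear class counterpart in 6.5.2. Tofacitinib may fall under the open-ended immunosuppressant line. Whether the residual line reaches either drug depends on approval status, which the documents do not give. In Table 5-1 that wording has its own row, with a washout of "12 weeks (or 5 half-lives, whichever is longer", which hints that it was not written for them. Exclusion criterion 18 does not settle it: for a participant who "receives prohibited concomitant treatments (see Section 6.5.2" it points back to the same list.

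**The case against.** **Use would be visible anyway.** Concomitant medication is summarised by ATC class and period and listed by participant, and important deviations are summarised by dose group (SAP 6.1.2, 6.1.4). With about 40 participants a case could be found by eye. This stands. What those outputs do not do is tie the start date to the Week 4 or Week 16 assessment, or separate the use from the response rate.

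**The stakes are low.** The endpoints are secondary and descriptive, with no testing. The intervals in Step 3 are 30.5 (98.8 − 68.3) to 45.6 (72.8 − 27.2) points wide, against a shift of 5 per participant. The exposure-response work has its own plan and may treat such data differently. PASI75 at Week 4 would need both use and effect within four weeks. All of this stands and keeps the point minor.

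**Stronger readings that the documents do not support.**

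- *Every user is counted as a responder.* No. A user who stops IMP before the time point, for instance after a 7.2 discussion, is already a nonresponder.
- *The PK-PPS is certain to miss these participants.* This cannot be said without the Protocol Deviation Assessment Plan.
- *Apremilast is allowed on study.* A reader might infer this from 6.5.1, where medication is "permitted during this study as long as medications are not explicitly prohibited by the protocol". That sentence concerns medical conditions and adverse events. The psoriasis treatments that 6.5.1 allows are topical or scalp products and emollients. Protocol 2.3 withdraws participants who are not benefitting "so that they can receive the appropriate alternate therapy outside of the study", and only in the safety follow-up does Protocol 6.8 say "the Investigator may consider standard of care for PSO treatment after discussion with the Medical Monitor or UCB Study Physician". The intent to prohibit is evident, and item 8 leads to the same discussion as item 9. The list gap has no effect on the analysis.

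**Conclusion.** The point holds for participants who stay on IMP and for the three binary secondary endpoints. Following the plan exactly, a response observed after starting another systemic antipsoriatic, or another psoriasis treatment prohibited by 6.5.2, counts as a bimekizumab response. Neither sensitivity analysis, by its SAP definition, changes that.

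It is minor: 5 percentage points per flipped participant at 20 per arm, with use probably rare. This rests on reading the PK-PPS from the SAP alone and on assumed frequencies of use. It does not show that any result is biased or that the dose decision is unsafe, and the primary PK endpoint is not in question. The mismatch between Table 5-1 and 6.5.2 is close to editorial.

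**What to change.** **Main change, in the SAP.** From the concomitant medication data, flag any systemic antipsoriatic or other psoriasis treatment prohibited by 6.5.2 that was started before Week 4 (for PASI75) or before Week 16 (for PASI90 and IGA 0/1). Report the counts by dose group. If any count is nonzero, add a sensitivity analysis that treats those participants as nonresponders. If all are zero, say so and stop.

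The cost is one derived flag, one count by dose group and at most one small extra table, with no new data collection.

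**Optional tidy-up, in the protocol.** Name apremilast, tofacitinib and any other systemic antipsoriatic, approved or investigational, in 6.5.2 to match Table 5-1, and keep the Section 6.8 allowance during safety follow-up. This is one line, but it needs an amendment with IRB/IEC approval. It is probably too late for the Initial Treatment Period, since the SAP version history already gives database lock as a reason for version 3.0.

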6.5.3 Vaccines

Administration of live (including attenuated) vaccines is not allowed during the conduct of the study and for 20 weeks after the final dose of IMP.

Administration of inactivated vaccines is allowed during the study at the discretion of the Investigator.

Administration of any other vaccine not mentioned above may be allowed following discussion with the Medical Monitor.

6.6 Dose modification

Dose modification during the study may occur under restricted circumstances.

No dose modifications are allowed during the Initial Treatment Period.

In the OLE Period (at Week 20 or later), participants whose weight increases to the next body weight category (ie, from <65kg to ≥65kg) will be administered the corresponding dose for ≥65kg body weight regardless of weight at Baseline. To prevent unnecessary switching of participants between weight categories, this change may only occur during the OLE Period after assessment of weight change by the Investigator at a scheduled clinic visit that is maintained for 2 consecutive weight assessments.

In the OLE Period, if a participant's body weight decreases from the ≥65kg to <65kg group, the participant should be discussed with the Medical Monitor to determine whether a dose adjustment is needed.

Once a study participant enters the OLE Period, and once the bimekizumab dose for PS0021 (the Phase 3 efficacy and safety study) has been selected, a study participant may switch to the selected PS0021 dose at the Investigator's discretion.

6.7 Criteria for study hold or dosing stoppage

UCB reserves the right to temporarily suspend or prematurely discontinue this study either at a single site, multiple sites, or at all sites at any time for reasons including, but not limited to, safety or ethical issues, inaccurate or incomplete data recording, noncompliance, or unsatisfactory enrollment with respect to quality or quantity.

If the study is prematurely terminated or suspended, UCB (or its representative) will inform the Investigators/institutions and the regulatory authority(ies) of the termination or suspension and the reason(s) for the termination or suspension, in accordance with applicable regulatory requirement(s). The Institutional Review Board (IRB)/Independent Ethics Committee (IEC) should also be informed and provided with reason(s) for the termination or suspension by the

Sponsor or by the Investigator/institution, as specified by the applicable regulatory requirement(s). In addition, arrangements will be made for the return or destruction of all unused IMP and other material in accordance with UCB procedures for the study.

6.8 Treatment after the end of the study

Study participants will be scheduled to have the SFU Visit 20 weeks after the final injection of IMP (the final dose of IMP may be administered in the Initial Treatment Period or in the OLE Period). During the SFU, if study participants' PSO deteriorates, the Investigator may consider standard of care for PSO treatment after discussion with the Medical Monitor or UCB Study Physician. Note that the half-life of bimekizumab must be considered in selection of appropriate PSO treatments during the SFU Period. All concomitant medications and PSO interventions administered during the SFU will be recorded on the appropriate eCRF pages.

7 DISCONTINUATION OF STUDY MEDICATION AND PARTICIPANT DISCONTINUATION/WITHDRAWAL

7.1 Discontinuation of study medication

Investigational medicinal product should be stopped if the study participant develops a medical condition, AE, or laboratory abnormality that, in the opinion of the Investigator, compromises the safety of the study participant or his/her ability to continue participation in the study.

In particular, IMP must be stopped if the study participant meets a laboratory value meeting stopping criteria (Section 7.1.1 and Section 7.1.2) or in situations described in Section 7.2.

Study participants who are permanently discontinued from IMP should be encouraged by the Investigator to return for all scheduled visits through Week 20 and should be asked to return for a SFU Visit 20 weeks after the final dose of IMP. Any study participant who discontinues IMP but continues in the study should be discussed with the Medical Monitor or UCB Study Physician.

In all cases, the study participant should be followed until the condition has resolved, and the Investigator should make an effort to reach the participant, as described in Section 7.3. Investigators should contact the Medical Monitor and/or UCB Study Physician, in advance whenever possible, to discuss potential withdrawal of a study participant.

7.1.1 Potential drug-induced liver injury IMP discontinuation criteria

Study participants with potential drug-induced liver injury (PDILI) must be assessed to determine if IMP must be discontinued. In addition, all concomitant medications and herbal supplements that are not medically necessary should also be discontinued.

7.1.1.1 PDILI discontinuation criteria

The PDILI criteria below require immediate discontinuation of IMP for study participants with any of the following:

- ALT or AST $\geq 8 \times \text{ULN}$
- ALT or AST $\geq 3 \times \text{ULN}$ and coexisting total bilirubin $\geq 2 \times \text{ULN}$
- Study participants with ALT or AST $\geq 3 \times \text{ULN}$ who exhibit temporally associated symptoms of hepatitis or hypersensitivity. Hepatitis symptoms include fatigue, nausea, vomiting, right

upper quadrant pain or tenderness. Hypersensitivity symptoms include fever (without clear alternative cause), rash, or eosinophilia (ie, >5%).

If a nondrug-related cause for the symptoms can be confirmed, these study participants may resume IMP administration after discussion with the Medical Monitor and/or UCB Study Physician, but only when the requirements for rechallenge with IMP as provided in Section 10.6.2 are followed.

The PDILI criterion below allows for study participants to continue on IMP at the discretion of the Investigator.

- Study participants with ALT or AST $\geq 5 \times \text{ULN}$ and $< 8 \times \text{ULN}$, total bilirubin $< 2 \times \text{ULN}$, and no eosinophilia (ie, $\leq 5\%$), with no fever, rash, or symptoms of hepatitis (eg, fatigue, nausea, vomiting, right upper quadrant pain or tenderness).

Evaluation of PDILI must be initiated as described in Appendix 6 (Section 10.6) with repeat tests performed in 2 weeks. Upon re-test, if ALT or AST values have reduced to $< 5 \times \text{ULN}$, the study participant can continue with the study. However, if ALT or AST remains $\geq 5 \times \text{ULN}$ and $< 8 \times \text{ULN}$ after re-test, IMP should be temporarily withheld and study participant should undergo a repeat test in 2 weeks. If ALT or AST values remain $\geq 5 \times \text{ULN}$ even after the second re-test, then the study participant should be permanently withdrawn from IMP and should be followed for possible PDILI.

If study participants are unable to comply with the applicable monitoring schedule, IMP must be discontinued immediately.

Investigators should attempt to obtain information on study participants in the case of IMP discontinuation to complete the final evaluation. Study participants with PDILI should not be withdrawn from the study until investigation and monitoring are complete. All results of these evaluations and observations, as well as the reason(s) for IMP discontinuation and study participant withdrawal (if applicable), must be recorded in the source documents. The eCRF must document the primary reason for IMP discontinuation.

